7.2.2 ELISA (IgG) Concentration and MN_{50} Titers for SARS-CoV-2

Serum (IgG) antibody responses (ELISA) for vaccine homologous SARS-CoV-2 rS antigen and cross-reactive virus variants, if available, will be conducted. For the serum IgG antibody levels specific for the rS antigen(s) as detected by ELISA, the derived/calculated endpoints of IgG antibody response will include: GMEU, GMEUR, $GMFR_{Post/Pre}$, SCR, which will be calculated in manner similar to HAI antibodies described above. Further description of the analyses for GMEUR appear at the end of this section.

MN_{50} antibody responses for vaccine homologous SARS-CoV-2 rS antigen and cross-reactive virus variants, if available, will be conducted. The derived/calculated endpoints of MN_{50}

antibody responses specific for SARS-CoV-2 wild-type will include the same assessments of GMT, GMFR_{Post/Pre}, GMTR, SCR as HAI antibody response.

The definition of seroconversion is a post-vaccination concentration/titer \geq 4-fold higher than baseline. Participants indicating evidence of infection with SARS-CoV-2 prior to the time point analyzed may be excluded from the calculations. This will be determined by examining the anti-NP results taken at Day 70 and/or Day 182. An alternative measure, seroresponse, may be explored which is defined as participants having a value or fold-rise greater than the 95th percentile of values in a reference group, which would be chosen if this analysis is performed and described in the study report.

Between-group GMEUR of IgG and MN antibodies to SARS-CoV-2 will be calculated at post-vaccination time points (adjusted for intergroup variation in baseline [pre-vaccination] values) and two-sided 95% CI will be calculated on log-transformed values using the analysis of covariance (ANCOVA) with the study vaccine group and baseline (Day 0) measurement as the covariates under two-sided type I error rate of 0.05. No type I error rate will be adjusted.

- Groups A-N (experimental vaccine) individually after 1 dose at Day 28 to Group P (reference vaccine) after 1 dose at Day 28
- Groups A-N (experimental vaccine) individually after 2 doses at Day 70 to Group P (reference vaccine) after 2 doses at Day 70

Two-sided 95% CIs of the difference in SCRs for IgG and MN antibodies to SARS-CoV-2 for the above cited comparisons of GMEUR will be based on the Miettinen and Nurminen method with the following sample SAS code:

```
proc freq data=SARSdata;
  by Visit;
  tables trtarm*scr / missing riskdiff (cl=MN);
run;
```

Graphical presentations of the data (e.g., reverse cumulative distribution curves, boxplots, correlation plots) may be generated.

7.3 Analysis of Exploratory Immunogenicity Endpoints

CMI responses to the various formulations/regimens in terms of peripheral blood CD4+ T cells which express one or more cytokines or activation markers (e.g. CD40L, INF-gamma, IL-2, TNF-alpha, IL-13) in response to in-vitro stimulation with strain-specific HA or rS will be assessed. Analysis of exploratory CMI response endpoints will be performed on a subset of approximately 50% of all participants chosen based on site location and feasibility of testing at Days 0, 7, 63 and 182 measured by ICCS and/or ELISpot assay. CMI results may be reported as an addendum to the main CSR.

The analysis for CMI response may include:

- Counts and/or proportions at Day 0, 7, 63, and 182 will be summarized by study vaccine, strain, and visit.

- Geometric mean counts (GMC) calculated as the antilog of the mean of the log-transformed counts at Day 0, 7, 63, and 182 will be summarized by study vaccine, strain, and visit.
- Geometric mean fold rise (GMFR) of counts between post-vaccination (Day 7/63/182) and pre-vaccination (Day 0) will be summarized by study vaccine, strain, and visit.
- GMCR – between-group ratio of geometric mean of counts for interested comparisons at Day 7, 63, and 182, adjusted for intergroup variation in baseline [pre-vaccination] counts.
 - The log10 values will be used to construct a 95% CI using the analysis of covariance (ANCOVA) with the study vaccine group and baseline at Day 0 as the covariates

Graphical presentations of the analyses (e.g., boxplots, bar graphs with corresponding 95% CIs, reverse cumulative distribution curves) may be generated.

Further details for data handling of CMI data will be provided by Novavax laboratory scientists at the time of analysis. Examples include LLOQ values for individual cytokines, whether background values need to be subtracted, handling zero or negative counts, and units for reporting.

Immune response to the various formulations/regimens in terms of human angiotensin-converting enzyme 2 (hACE2) inhibition antibodies will be analyzed descriptively in a manner similar to the summaries described for IgG antibody concentration and MN₅₀ antibody titers for SARS-CoV-2 (reference Section 7.2.2).

7.4 Analysis of Immunogenicity Endpoint Using the DoE Approach

The study's 12 unique vaccine formulations (excluding reference formulations) arose from a DoE approach with the objective to construct one or more response surface models that can provide information on combination(s) of antigen quantities (both HA and rS) that when combined with 50 µg of Matrix-M1 adjuvant will maximize HAI and anti-S immune responses. The combination(s) identified may or may not be the formulations that are currently being studied. The goal of response surface modelling is to establish the relationship between response and one or more factors, using a set of tools to identify factor settings which optimize response. The results are intended to inform selection of potential dose levels for further study. The modelling exercise will consist of a prospectively established set of analyses and may be followed by further exploration. The SAP defines the prospective set of analyses, whereas further exploratory modelling will be described in the clinical study report.

Day 28 (post single dose) and Day 70 (post 2 doses) immune responses will be the data of primary interest for the regression analysis. Participants in the study are baseline seropositive for SARS-CoV-2 and can be expected to have previously exposure to influenza viruses, so baseline antibody levels for the response parameters are likely to vary and be predictive of response at Days 28/70. Therefore, participants with non-missing Day 28/70 and baseline values in the PP Analysis Set for the responses of interest (Section 7.3.1) will be included in the modeling. In response surface modelling, treatment group is not explicitly designated as an independent variable but are indirectly reflected by factor levels that account for the

amount of each antigen (HA or rS) received. These are treated mathematically as coded continuous quantities ranging from -1 to 1. Participants having a lab-confirmed case of influenza (determined via examination of adverse event reporting) or COVID-19 (determined by anti-NP) between Day 0 and Day 70 may be excluded for the modeling to reduce the extra variability arising from such data points.

To incorporate variation in baseline antibody levels, the individual participant fold-rise in anti-spike and HAI antibody responses at each time point (Table 4) would be used to build predictive model(s). However, examination of the data may reveal that using absolute value is more appropriate, with or without considering the baseline value as a predictor. The starting point is a full model that will include all main effects, interactions, and quadratic effects.

Table 4 List of Responses for Response Surface Modelling

Response	Transformation	Goal
Fold-rise (or absolute value) of HAI titer to A/Brisbane/02/2018 [H1N1] pdm09 (homologous strain) at Day 28 relative to Day 0	Logarithm	Maximize
Fold-rise (or absolute value) of HAI titer to A/Kansas/14/2017 [H3N2] (homologous strain) at Day 28 relative to Day 0	Logarithm	Maximize
Fold-rise (or absolute value) of HAI titer to B/Maryland/15/2016 [Victoria] at Day 28 relative to Day 0	Logarithm	Maximize
Fold-rise (or absolute value) of HAI titer to B/Phuket/3073/2013 [Yamagata] at Day 28 relative to Day 0	Logarithm	Maximize
Fold-rise (or absolute value) of IgG by ELISA to SARS-CoV-2 rS at Day 28 relative to Day 0	Logarithm	Maximize
<hr/>		
Fold-rise (or absolute value) of HAI titer to A/Brisbane/02/2018 [H1N1] pdm09 (homologous strain) at Day 70 relative to Day 0	Logarithm	Maximize
Fold-rise (or absolute value) of HAI titer to A/Kansas/14/2017 [H3N2] (homologous strain) at Day 70 relative to Day 0	Logarithm	Maximize
Fold-rise (or absolute value) of HAI titer to B/Maryland/15/2016 [Victoria] at Day 70 relative to Day 0	Logarithm	Maximize
Fold-rise (or absolute value) of HAI titer to B/Phuket/3073/2013 [Yamagata] at Day 70 relative to Day 0	Logarithm	Maximize
Fold-rise (or absolute value) of IgG by ELISA to SARS-CoV-2 rS at Day 70 relative to Day 0	Logarithm	Maximize

Further exploratory modelling may be performed on cell-mediated immunity (CMI) response measures (e.g. homologous SARS-CoV-2 spike-specific or specific HA T-cell counts), as well as antibody responses tested with different assays (e.g. neutralization titers) or on drift strains. These analyses would be specified in a separate document and described in the clinical study report.

There are 2 factors studied (Table 5)—the nominal amount (in μg) of SARS-CoV-2 rS protein in each dose, and the nominal amount (in μg) of each of four (4) HA strains for influenza strains in each dose.

Table 5 List of Factors in Design of Experiments Approach

Factor (unit)	Role	Lower value	Upper value
SARS-CoV-2 rS (μg)	Continuous	2.5	22.5
HA per strain (μg)	Continuous	5	60

Table 6 shows the planned list of runs identified by the DOE platform within SAS JMP and number of planned replicates per run. The actual number of replicates providing data will be dependent on the enrollment into the study and exclusion of subjects from the PP Analysis Set. Runs 1 and 3, as well as 8 and 14, are identically specified.

Table 6 Planned List of Runs

Run	Replicates	Value for SARS-CoV-2 Factor	Value for HA Factor
1	40	22.5	60
2	40	2.5	10
3	40	22.5	60
4	40	7.5	10
5	40	22.5	10
6	40	7.5	35
7	40	22.5	5
8	40	2.5	60
9	40	7.5	5
10	40	2.5	5
11	40	22.5	35
12	40	2.5	35
13	40	7.5	60
14	40	2.5	60

Factor levels are treated as continuous coded values ranging from -1 to 1 so that each factor contributes equally to predicting the optimal response. The initial full regression model to be run is expressed as:

$$Y = \beta_0 + \beta_1 X_1 + \beta_2 X_2 + \beta_3 X_1 X_2 + \beta_4 X_1^2 + \beta_5 X_2^2 + \varepsilon$$

where:

Y is the response

X1 = coded antigen level for each HA flu strain

X2 = coded antigen level for SARS-CoV-2 rS

X1*X2 = interaction term for HA antigen level and SARS-CoV-2 rS antigen level

ϵ = error term with expected value of 0

SAS JMP will be used to fit a least-squares model for each response indicated in Table XX. Each run's replicate values may or may not be averaged across the subjects in the PP Analysis Set to determine the independent Y value for the run. An examination of the data will guide the decision and it will be documented in the report. Baseline measurement for each replicate may be included as covariate if no averaging is performed for a run's replicates. The initial full model will be run and significance of each term examined. A p-value <0.05 indicates that a term is significant. Non-significant terms will be removed and the resulting reduced model (for each response) will be fitted for exploration with a Predication Profiler tool. Desirability functions (ranging from 0 for lowest level to 1 for highest level) will be used to identify factor settings that optimize the set of responses. Weighting for each response may be considered. Factor setting(s) that lead to the highest overall desirability will be the level of HA and rS that optimize responses in Table XX.

As a parallel analysis, SAS PROC RSREG will be used to run a response surface model that uses the dataset without first averaging the results of each run across replicates nor incorporating the baseline measurement into a fold-rise (i.e. use the data as-is). In this model, Y would be set as the antibody response value at the time point of interest, with BL being the corresponding measurement at Day 0. X1 and X2 have the same definition as the when the model is fitted within SAS JMP.

Example SAS code:

```
PROC RSREG DATA=X;  
MODEL Y=BL X1 X2 / LACKFIT COVAR=1;  
RUN;
```

The fit of the model is to be assessed by examining the p-value from the lack-of-fit test and plots of residuals for each factor. Significance of main, quadratic and interaction effects will also be assessed and reported.

The canonical analysis results from PROC RSREG provide information on the shape of the response surface. A maximum point is identified on the response surface by all eigenvalues being negative (a second order derivative test).

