## 6.2 Immunogenicity Assessments

Blood samples for immunogenicity assessments will be collected before vaccination (Day 0) and at selected time points following vaccination (Table 1). As a secondary objective, serum HAI antibody response (assayed with wild-type VLP reagents) at Day 28 (post-first dose of trial vaccine), Day 56, and Day 70 (post-second dose of trial vaccine) and at other follow-up time points, against 4 vaccine-homologous strains, and at least 1 antigenically drifted A or B strain will be assessed. In addition, neutralizing antibody responses (assayed with wild-type virus) against 4 vaccine-homologous strains, and at least 1 antigenically drifted A or B strain will be conducted. Serum (IgG) antibody responses (ELISA) for vaccine homologous SARS-CoV-2 rS antigen and cross-reactive virus variants, if available, will be conducted. CMI responses to the various formulations/regimens in terms of peripheral blood CD4+ T cells which elaborate one or more cytokines or activation markers (eg, IL-2, TNF $\alpha$ , IFN $\gamma$ , or CD40L) produced after in vitro stimulation of peripheral blood mononuclear cells (PBMCs) will be assessed at selected time points in all participants at a selected subset of sites. Aliquots of all collected samples from this study may be retained for additional testing of antigens specific to influenza HA or SARS-CoV-2 (or related variants), or for assay development or qualification for other pathogens (excluding HIV) for a maximum of 25 years (starting from the date at which the last participant had the last study visit), unless local rules, regulations, or guidelines require different timeframes or different procedures, in accord with participant consent. Retained sera may also be used for clinical laboratory testing for safety if needed to evaluate an AE.

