### **9.3.8 Predictive Modeling of the Measured Responses**

The Day 70 immune responses will be the primary set of data to use for stepwise multi-regression analysis. Participants with non-missing Day 70 responses will be included in the modeling. The PP Analysis Set will be used, meaning participants receiving both doses of study material. Treatment group is not part of the model independent variables (“factors” and their higher order terms), but rather the factors account for the amount of each antigen or adjuvant received, treated mathematically as continuous quantities.

Participants having a lab-confirmed case of influenza or COVID-19 between Day 0 and Day 70 may have data excluded for the modeling to reduce the extra variability arising from such data. The input data may be assessed for extent and nature of variability to determine which data points to exclude. Sensitivity analyses may need to be performed during the modelling exercise to assess impact of selected data points on the conclusions.

Response measures of interest will be defined in the SAP. Each of these responses will be modelled with the levels of nominal antigen/adjuvant for the formulation as independent variables. The significance of each model parameter will be assessed to determine whether to keep the parameter in the model (eg, interaction terms). The end result will include predictive models, a list of significant terms, and optimized dosage of antigen/adjuvant combinations that maximize the desirable responses.

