- SCR – defined as proportion of participants with either a baseline reciprocal (Day 0) titer of < 10 and a post-vaccination reciprocal titer ≥ 40 , or a baseline reciprocal (Day 0) titer of ≥ 10 and a post-vaccination titer ≥ 4 -fold higher than the baseline titer as measured on Days 28, 56, 70, 84 and 182.
- SCR and corresponding 2-sided exact binomial 95% CIs will be calculated using the Clopper-Pearson method with the following sample SAS code:

```
proc freq data=HAIdata nopolish;  
  by Treatment Visit;  
  tables seroconvind / binomial(exact) alpha=.05;  
  output out=out1 binomial;  
  
run;
```

- Two-sided 95% CIs of the difference in SCRs in HAI titers for the above cited comparisons of HAI GMTR will be based on the Miettinen and Nurminen method with the following sample SAS code:

```
proc freq data=HAIdata;  
  by Visit;  
  tables trtarm*scr / missing riskdiff (cl=MN);  
run;
```

- SPR – defined as the proportion of participants with a reciprocal HAI titer ≥ 40 on Days 28, 56, 70, 84 and 182.
 - SPR and corresponding 2-sided exact binomial 95% CIs will be constructed similarly using the Clopper-Pearson method.

The derived/calculated endpoints of MN_{50} antibody responses specific for the influenza HA will include the same assessments of GMT, $GMFR_{Post/Pre}$, GMTR, SCR, SCR differences, and SPR as for HAI antibody response.

Graphical presentations of the data (e.g., reverse cumulative distribution curves, boxplots, correlation plots) may be generated.

Participants indicating a lab-confirmed episode of influenza prior to the visit being analyzed may be excluded from the calculations. If this is implemented, it will be determined via a review of unsolicited adverse event data.

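### SAP 7.4 applies one Day 0–70 infection exclusion to every response-surface model, although half the modelled responses are at Day 28, and it does not match the virus to the response

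*SAP*

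**What the plan says.** SAP 7.4 states that "Day 28 (post single dose) and Day 70 (post 2 doses) immune responses will be the data of primary interest for the regression analysis". Table 4 lists ten responses, five at each time: HAI to the four vaccine strains, and anti-S IgG. One Day 28 entry is "Fold-rise (or absolute value) of IgG by ELISA to SARS-CoV-2 rS at Day 28 relative to Day 0".

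The same section then gives a single exclusion for the modelling as a whole: participants with lab-confirmed influenza (found from adverse event reports) or "COVID-19 (determined by anti-NP) between Day 0 and Day 70 may be excluded for the modeling to reduce the extra variability".

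Protocol 9.3.8 has the same window: "Participants having a lab-confirmed case of influenza or COVID-19 between Day 0 and Day 70 may have data excluded for the modeling". It names Day 70 as the primary data for the modelling and does not mention Day 28.

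The group summaries follow a different rule. For influenza titres, SAP 7.2.1 says "Participants indicating a lab-confirmed episode of influenza prior to the visit being analyzed may be excluded from the calculations". For SARS-CoV-2 responses, SAP 7.2.2 says "Participants indicating evidence of infection with SARS-CoV-2 prior to the time point analyzed may be excluded from the calculations". Protocol 9.3.7.1 and 9.3.7.2 likewise limit exclusion to cases between vaccination and the time point analysed, with influenza for the influenza assays and COVID-19 for the SARS-CoV-2 assays.

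The schedules of events in both documents draw anti-NP on Days 0, 70 and 182 only. Serum for ELISA and HAI is also drawn on Day 28.

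**The concern.** An infection after the Day 28 sample cannot have changed the Day 28 titre. Removing that value does not serve the rule's stated aim of reducing variability and only loses information. The window fits the Day 70 response in Protocol 9.3.8. The SAP adds Day 28 as a second primary time and keeps the window, and SAP section 12 (changes from the protocol) lists neither the added time point nor any adjustment of the rule.

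The rule also pools the two viruses. Read literally, a COVID-19 case can be taken out of the HAI models and an influenza case out of the anti-S model, at Day 70 as well as at Day 28.

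These models matter. SAP 7.4 removes terms that do not reach p < 0.05 and uses the fitted surfaces to locate the antigen levels with the highest overall desirability. Avoidable loss of data, or selection on an event after the sample, feeds into that choice.

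**Working it through.** **The plan's own figures.** The plan gives no figure for infections or for values lost to this rule. The nearest is the informal power statement in SAP 1.2 (above 99% for a two-fold difference with 40 per group). It cannot be reproduced, because no standard deviation is given. At two-sided 5% it would need a log10 SD of about 0.314 or less. Nothing below depends on it.

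**Inputs from the documents.** 14 combination arms × 40 = 560 participants (SAP Tables 1 and 6). Sampling is at Days 28 and 70, and anti-NP is drawn on Days 0, 70 and 182. Nominal days are used and visit windows ignored.

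**Assumed inputs.** 5–20% infected by Day 70, at an even rate over the 70 days. The documents give no infection rate.

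**Step 1: share of the window after the Day 28 sample.** (70 − 28)/70 = 42/70 = 60%.

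**Step 2: Day 28 values lost to later infections.** 560 × p × 0.60:

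| Infected by Day 70 | Infected after Day 28 | Lost of 560 | Lost per 40 |
|---|---|---|---|
| 5% | 3% | 16.8 | 1.2 |
| 10% | 6% | 33.6 | 2.4 |
| 20% | 12% | 67.2 | 4.8 |

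**Step 3: precision.** Take Day 28 anti-S and suppose all infections are COVID-19. The rule as written leaves a fraction 1 − p. A rule limited to infections before Day 28 leaves 1 − 0.4p. The standard error ratio is √[(1 − 0.4p)/(1 − p)]: √(0.98/0.95) = 1.016 at 5% and √(0.92/0.80) = 1.072 at 20%.

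**Step 4: possible bias in Day 28 anti-S.** Further assumptions: normal log10 response with SD 0.5; a true difference of 0.30 between two rS levels; and a logistic risk of infection after Day 28 that averages 3–12% over the two arms, with log-odds slope −1 or −2 per log10. Comparing the arm means among the uninfected by numerical integration gives:

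| Slope | 3% after Day 28 | 12% after Day 28 |
|---|---|---|
| 0 | 0.300 | 0.300 |
| −1 | 0.298 | 0.293 |
| −2 | 0.292 | 0.277 |

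The attenuation is about 1–8%. As a rough check, the loss is close to |slope| × SD² × (risk in the lower arm − risk in the higher arm). For slope −2 and 12% the arm risks are 14.8% and 9.2%, so 2 × 0.25 × 0.056 = 0.028, slightly more than the integrated loss of 0.023. With no dependence on the response there is no bias.

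**Step 5: fold-rise instead of absolute titre.** Fold-rise is the default in SAP 7.4. Let risk follow the Day 28 titre, give baseline and rise an SD of 0.5 each, and assume a correlation between them of −0.5 to −0.8. With the risks (here set in the lower arm) and slopes of Step 4, the 0.30 becomes 0.290–0.300 (0–3%).

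**Step 6: can the infection be dated?** A conversion between the Day 0 and Day 70 anti-NP samples cannot be placed before or after Day 28 by that assay. Rewording the window is therefore not enough for Day 28 anti-S.

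**The case against.** The strongest reply is that the rule is permissive. Exclusion is allowed, not required, and its stated purpose is to limit variability caused by the infection, which does not reach a sample taken beforehand. Protocol 9.3.8 also speaks of choosing which data points to exclude and foresees sensitivity analyses. This stands in part: the loss is possible, not certain. But SAP 7.4 gives no criterion for using the discretion, and its window is wider than the one the SAP uses for its other immunogenicity analyses.

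A reader might infer that low responders are removed preferentially, so that the rS dose effect is flattened across half of the modelled responses. The documents do not support that. They state no link between response and infection. Four of the five Day 28 responses are HAI, and COVID-19 risk driven by anti-S is not selection on HAI. The second dose at Day 56 falls inside the Day 28–70 interval and weakens any link to the Day 28 level. The default response is fold-rise, for which the effect is smaller still. An 11% attenuation appears only if 20% are infected after Day 28, whereas 5–20% by Day 70 means 3–12%.

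It is also fair to say that one wide window is a cautious choice when infections cannot be dated. Making no infection exclusion at Day 28 would keep every infection before that sample. With 2–8% infected by then, an assumed 0.6 log10 boost and the same slopes, the 0.30 difference becomes about 0.28–0.30. That is a distortion of similar size in the same direction, so dropping the exclusion altogether is not a sound remedy for anti-S.

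**Conclusion.** The point holds as a mismatch between the exclusion rule and the responses it covers. The Day 0–70 window in SAP 7.4 does not suit the five Day 28 responses, and it ignores which virus bears on which antibody. SAP 7.2.1 and 7.2.2 and Protocol 9.3.7 set exclusion by time and by virus.

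If the rule is applied as written, the clear cost is precision: about 17–67 of 560 participants dropped from the Day 28 models for later infections, given 5–20% infected by Day 70 at an even rate. Bias is a secondary possibility. It concerns mainly Day 28 anti-S, one response of ten, and needs infection risk to depend on that response. Under the assumed slopes it is about 1–8% of a 0.30 log10 difference, and less for fold-rise. The results are meant to inform dose levels for further study, with confirmation planned in a later Phase 2 trial. That limits the consequence but does not justify a rule that is easily corrected.

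**What to change.** In SAP 7.4, define the exclusion for each response: only infection with the matching virus (influenza for HAI, SARS-CoV-2 for anti-S) before that response's sample. That means Day 0–28 for the Day 28 models and Day 0–70 for the Day 70 models. Record the change in SAP section 12, and settle it before the exclusions are fixed for the Day 70 unblinding described in SAP 1.4.

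For Day 28 anti-S, test retained Day 28 serum for anti-NP in participants who convert between Day 0 and Day 70, and exclude only those already converted at Day 28. Protocol 6.2 provides for such testing, subject to participant consent: "Aliquots of all collected samples from this study may be retained for additional testing of antigens specific to influenza HA or SARS-CoV-2". If this is not done, date cases from PCR or adverse event records where available, and report the Day 28 anti-S model with and without the converters who cannot be dated.

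The cost is a wording change plus either a few assays on stored serum or one extra sensitivity run.
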